## **Description of Measures**

*Enrollment Screening:* Patient demographic information, past medical history, weight, history of pain, prior treatments, and any secondary diagnoses will be recorded to ensure the patient is a candidate for the trial.

Informed Consent Discussion: Doctor or study staff will explain the research, go through corresponding research subject consent form, and answer patient questions.

(Disabilities of the Arm, Shoulder, and Hand (DASH) and Patient-Rated Tennis Elbow Evaluation (PRTEE)): Patient will report the difficulty in performing various activities, elbow-related quality of life, and the level of pain experienced in the previous week.

Visual Analog Scale  $(VAS)^{20}$ : Patient will self-report pain level in the shoulder on a 0-10 scale at the same time each day for consistency.

Patient Specific Functional Score: Patient will identify and score up to three important activities they are unable to do or have difficulty doing due to elbow injury.

Hand Grip Strength Test: Doctor or study staff will measure the patient's grip strength with a dynamometer.

Device Usage Log: Patient will self-report device usage, including time of therapy initiation, time of therapy completion, and device location.

Medications Log: Patient will self-report medication intake, including type and quantity.

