### 4. HYPOTHESIS

Subjects who are assigned and compliant to wearing the semiconductor embedded arm sleeve will experience improved outcomes in symptoms, pain management, and elbow function throughout the course of the study compared to the patients assigned to wear and compliant with wearing the placebo sleeves.

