## **Secondary Outcomes**

- 1. Reduction in pain as determined by Numeric Pain Rating Scale or Visual Analog Scale (VAS) compared to placebo group.
- 2. Improvement in patient function as determined by Patient Specific elbow PROMIS score (Disabilities of the Arm, Shoulder, and Hand (DASH) and Patient-Rated Tennis Elbow Evaluation (PRTEE)) and the patient specific functional score compared to control and placebo groups.
- 3. Reduction in symptom severity upon physical examination and improvement in grip strength compared to placebo group.

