## **Exclusion Criteria**

- 1. Patient has a history of neurological conditions, including multiple sclerosis or Parkinson's disease
- 2. Patient has severe medical condition, including recent myocardial infarction, unstable angina, heart failure, severe anemia
- 3. Patient has had prior surgical treatment of the elbow in the last 5 years or injection treatment(s) in the last 2 years
- 4. Patient has complete tear of ECRB tendon or other surgical indication
- 5. Patient has chronic pain conditions unrelated to elbow condition
- 6. Patient has auto-immune or auto-inflammatory diseases
- 7. Patient has used tobacco within the last 90 days
- 8. Patient is not within the ages of 18-65
- 9. Patient has a history of metabolic disorders
- 10. Patient has an active infection (local or systemic)
- 11. Patient is unwilling or unable to sign the corresponding research subject consent form

12. Patient meets any other criteria or has any other condition that, in the opinion of the investigator, would prevent them from completing the study or that, in the opinion of the investigator, would confound study results.

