## **Study Measures**

Subjects will complete a variety of repeated subjective and objective measures throughout the course of the study. A schedule of study-related events can be found in Table 1.

TABLE 1	Enrollment Visit	2-Week Follow-Up Phone Call	4-Week Follow- Up Phone Call	8-Week Follow- Up Visit	3 Month Follow-Up Phone Call	6 Month Follow-Up Visit	*Daily Reported
Enrollment Screening	X						
Informed Consent Discussions	X						
PROM Scores 	X	X	X	X	X	X	
Numeric Visual Analog Scale 	X	X	X	X	X	X	X
Patient Specific Functional Score 	X	X	X	X	X	X	
PFG Measurement (Grip Strength Test) 	X			X		X	
Device Usage Log							X
Medications Log							X

\*Daily reported measures will only be required up to the 8-week timepoint.

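### The pain scale for secondary outcome 1 is described as rating the shoulder in an elbow trial, and the examination half of secondary outcome 3 is neither scheduled nor described

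*Protocol*

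**What the plan says.** **Pain.** Secondary outcome 1 is "Reduction in pain as determined by Numeric Pain Rating Scale or Visual Analog Scale (VAS) compared to placebo group". It names no body site. Table 1 (Study Measures) lists one row for a numeric visual analog scale at every contact and daily, with daily reporting required only to week 8. It names no site either. Description of Measures has one entry for the scale: "Patient will self-report pain level in the shoulder on a 0-10 scale at the same time each day for consistency".

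**The rest of the Protocol** is about the elbow. The Hypothesis expects "improved outcomes in symptoms, pain management, and elbow function throughout the course of the study". In Description of Measures, the DASH/PRTEE entry covers "elbow-related quality of life, and the level of pain experienced in the previous week", and the Patient Specific Functional Score asks for "important activities they are unable to do or have difficulty doing due to elbow injury".

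**Examination.** Secondary outcome 3 is "Reduction in symptom severity upon physical examination and improvement in grip strength compared to placebo group". Table 1 has a row beginning "PFG Measurement (Grip Strength Test", marked at enrollment, 8 weeks and 6 months, and Description of Measures says that grip is measured with a dynamometer. Neither place mentions a physical examination.

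**The concern.** There are two separate defects, and the first is the more serious.

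The first is a misstatement. The one sentence that tells staff what the pain scale records points to a joint that the trial does not study. If the diary and visit forms were built from it, the ratings could not answer secondary outcome 1, and no analysis could repair them afterwards.

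The second is an outcome component with no planned data. A reduction in severity needs a baseline and at least one follow-up value on a defined scale, and the Protocol provides none of these for the examination. An SAP cannot fill either gap, because what subjects are asked and what is examined at which visit are data-collection procedures. This Protocol fixes those in Table 1 and Description of Measures.

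**Working it through.** There is no sample-size, power or error-rate figure to reproduce. The check sets the outcome list, the schedule and the descriptions side by side and counts entries.

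**Table 1** has 8 rows and 7 columns: 3 in-person contacts (enrollment, 8 weeks, 6 months), 3 phone calls (2 weeks, 4 weeks, 3 months) and 1 daily column. **Description of Measures** has 8 entries.

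| Measure | Outcome it serves | Marked in Table 1 | Described | Body site in description |
|---|---|---|---|---|
| PRTEE/DASH | Primary; secondary 2 | 6 of 6 contacts | Yes | Elbow |
| Patient Specific Functional Score | Secondary 2 | 6 of 6 contacts | Yes | Elbow |
| 0-10 pain scale | Secondary 1 | 6 of 6 contacts + daily = 7 of 7 columns | Yes | **Shoulder** |
| Grip strength | Secondary 3 | 3 of 6 contacts | Yes | Not applicable (hand grip) |
| Symptom severity on examination | Secondary 3 | **0 of 8 rows** | **0 of 8 entries** | None |

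**Pain scale.**

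1. Three places mention it: Secondary Outcomes, Table 1 and Description of Measures. Only the last names a site, and it names the shoulder.
2. Of the three self-report measures whose description names a site, two say elbow and one says shoulder. Elsewhere in the Protocol's own text, the word shoulder occurs only in the name of the DASH questionnaire.
3. The daily column alone covers 8 weeks × 7 days = 56 days per subject, in addition to the six contacts.
4. The exclusion "Patient has chronic pain conditions unrelated to elbow condition" should make chronic shoulder pain uncommon among those enrolled, so shoulder ratings would probably start low and have little room to fall. The Protocol gives no figure for this. It is supporting reasoning only.

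**Examination.**

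1. The enrollment screening entry lists demographics, history, weight, prior treatments and secondary diagnoses. It includes no symptom examination, so no baseline is specified.
2. The mild/moderate/severe grade under Study groups cannot stand in. It grades the extent of tendon tear rather than symptoms, is defined for block randomization, and is not scheduled at follow-up.
3. The section on IRB review, ethics and consent names the medical record and case report forms as data sources. Examination notes could reach the study that way, but the Protocol neither schedules them nor defines a score.

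**The case against.** The strongest reply is that the shoulder wording is an obvious slip. Everything else in the Protocol says elbow, the sentence is a protocol description rather than the diary text, and the diary and forms are not shown. The sentence also speaks of a daily rating, so extending it to the six contacts is an inference. Secondary outcome 1 names a numeric scale or a VAS, and only the VAS is described by name. The examination gap is a different kind of defect and should not borrow weight from the shoulder error; scoring rules may also sit in forms not seen. Finally, the primary outcome is intact, PRTEE/DASH records some pain at all six contacts, and grip strength remains assessable.

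Much of this stands as a limit on the consequence. It is probably a drafting error, whether any rating was affected is unknown, and the two parts should be weighed separately. It does not make the text right. The sentence is the sole operational description of the scale, the Compliance Statement commits investigators to follow the Protocol, and changes need IRB approval before they are implemented, so staff should not be left to correct it informally. The reach to all contacts rests on Table 1 giving the scale a single row with no second description. PRTEE/DASH is not the instrument named for secondary outcome 1. For the examination, unseen forms might contain a score, but a visit procedure that supports a named outcome belongs in the schedule, and it is absent there.

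**Conclusion.** Both parts hold, and the point should be fixed. The case rests mainly on the pain scale: its only description names the wrong joint, and that is certain from the text. The effect on data is not certain. It runs from none, if the forms already say elbow, to every rating on this scale across 7 of 7 Table 1 columns, if they copy the description. The upper end assumes that the single Table 1 row and the single description refer to the same instrument.

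The examination component is nearer to missing detail, but the gap is real: 0 of 8 rows and 0 of 8 descriptions, so the Protocol plans no data for it. The damage is confined to secondary outcome 1 and half of secondary outcome 3. The primary PRTEE outcome, collected at 6 of 6 contacts, is not affected.

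**What to change.** 1. In the VAS entry of Description of Measures, replace the shoulder with the affected elbow.
2. Check every diary page and case report form built from that entry. If any asked about the shoulder, record which form version was used and when, and do not report those ratings as secondary outcome 1.
3. For secondary outcome 3, choose one of two options. Either remove the examination component and keep grip strength, dating and justifying the removal before unblinded results are seen; or define a scored elbow examination, describe it, and add a Table 1 row at enrollment, 8 weeks and 6 months. The other three contacts are phone calls.
4. As tidying, use one name for the 0-10 pain scale in Secondary Outcomes, Table 1 and Description of Measures.

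The cost is a short amendment with the IRB approval that the Protocol requires before implementation, plus a form check. Removing the examination component needs no new procedure. Keeping it needs a defined score and a few minutes at three visits that already take place. A baseline cannot be recovered for subjects already enrolled without one.

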# **Statistical Analysis**

Relevant clinical variables and demographic characteristics will be summarized by standard descriptive summaries (e.g. means, standard deviations, minimums, maximums, confidence limits, percentiles).

#### 6. COMPLIANCE STATEMENT

This study will be conducted in full accordance with all applicable Federal and State laws and regulations including 45 CFR 46. All episodes of noncompliance will be documented. The investigators will perform the study in accordance with this protocol, will obtain consent, and will report unanticipated problems involving risks to subjects or others in accordance with Western IRB Policies and Procedures and all federal requirements. Collection, recording, and reporting of data will be accurate and will ensure the privacy, health, and welfare of research subjects during and after completion of the study.

#### 7. RISK AND SAFETY MANAGEMENT

This study utilizes a treatment with no demonstrated side effects. There is minimal risk involved with the treatment or evaluation of the subject associated with this study. The primary risk in this study is the identification of individuals. However, all project staff with access to study data are accustomed to working with PHI-related, identifiable data and have completed requisite human subjects and data protection training. Additionally, safeguards are in place that will limit access to project folders to only the individuals directly involved with data collection and analysis. Data are stored in a secure electronic folder on the PI's server, and patient identifiers will be securely stored

separately from other information in data sets. The data collected for the study will be stored in a secure electronic database to which only the investigators will have access. Data analysis will occur using de-identified methods.

### Monitoring/Reporting of AE/SAE

The adverse events associated with PRP injections include skin reaction and local injection site pain. There is minimal risk with the semiconductor sleeves and as such we do not expect any adverse events. The main risk with this type of study is breach of confidentiality through the potential identification of individuals included in the study. If a breach of confidentiality occurs, the principal investigator and the project team will work together to report it to the compliance office and IRB and will follow the appropriate procedures. However, all standard procedures will be followed to ensure data privacy is maintained, i.e., by storing data in a limited access secure folder that is on the PI's server.

# **Study Oversight**

If study data are requested for monitoring, auditing, or regulatory inspection, the principal investigator will provide them in a timely manner. The study investigators will address all possible concerns and safety issues are not anticipated. There are no reasons why this study would need to be prematurely terminated and therefore oversight is not applicable.

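### No scheduled contact or log asks about adverse events and oversight is declared not applicable, so an absence of recorded events would not be evidence of safety

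*Protocol*

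**What the plan says.** Section 7 of the protocol (Risk and Safety Management) opens with the premise "This study utilizes a treatment with no demonstrated side effects". Its subsection Monitoring/Reporting of AE/SAE states "The adverse events associated with PRP injections include skin reaction and local injection site pain", and of the sleeve "There is minimal risk with the semiconductor sleeves and as such we do not expect any adverse events". The only procedure there concerns data privacy: "If a breach of confidentiality occurs, the principal investigator and the project team will work together to report it to the compliance office and IRB". Study Oversight then concludes "There are no reasons why this study would need to be prematurely terminated and therefore oversight is not applicable".

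For data collection, Study Measures says "A schedule of study-related events can be found in Table 1". That table covers enrollment, weeks 2, 4 and 8, months 3 and 6, and a daily column. A footnote adds "Daily reported measures will only be required up to the 8-week timepoint".

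Two other places point the other way. In Section 6 (Compliance Statement) the investigators "will report unanticipated problems involving risks to subjects or others" under IRB policy and federal requirements. The section IRB Review/Ethics/Informed Consent says the study is consistent with Good Clinical Practice.

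**The concern.** The waiver of oversight assumes what a trial would normally check: because no reason to stop is foreseen, nobody is assigned to look for one. The schedule follows the same assumption. A subsection headed for adverse events names two reactions to the injections but gives no step for recording them or anything else that happens to a subject.

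Two things are at stake. If a subject develops, say, a skin problem under the sleeve, no scheduled question would bring it out. And a report of few or no adverse events would reflect, to an unknown extent, that nobody asked. The commitment to report unanticipated problems depends on someone learning of them first.

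**Working it through.** The protocol states no safety figure, so there is none to reproduce. The check is a reading of the schedule, followed by one illustration.

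**1. Table 1, row by row.** The eight rows are enrollment screening, consent discussion, PROM scores, pain scale, patient-specific functional score, grip strength, device usage log and medications log. Rows that ask about adverse events: 0 of 8.

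**2. Description of Measures.**
- The device log takes start time, end time and location of wear.
- The medications log takes type and quantity, not the reason for use.
- The questionnaires cover pain, function and elbow-related quality of life.
- No description contains a question about adverse events.

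**3. Exposure against coverage.** Study Design asks for at least 12 hours of wear a day, including overnight, for the whole study. Taking 6 months as 182 days, 182 × 12 = 2,184 hours per subject. The daily logs are required for 8 weeks, and 56 / 182 = 31% of that time. After week 8 only two contacts remain: a telephone call at 3 months and a visit at 6 months.

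**4. The passages side by side.** The Compliance Statement and the Good Clinical Practice commitment presuppose that problems will be noticed. Section 7 says they are not expected, gives a path only for privacy breaches, and sets oversight aside. A duty to report and a schedule with no question about events can coexist on paper, but the second gives the first nothing systematic to work with.

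**5. What zero recorded events would mean (illustration).** Let *p* be the true proportion of subjects with an event, *c* the share of those who come to be recorded, and *n* the number on the active sleeve. Then P(no event recorded) = (1 − *pc*)^*n*. The protocol gives none of these three. I assume *p* = 5%. I take *n* = 40, which is half of the minimum of 80 under an assumed 1:1 allocation (no ratio is stated), and show *n* = 20 and 80 as the range.

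| Share recorded (*c*) | *n* = 20 | *n* = 40 | *n* = 80 |
|---|---|---|---|
| 100% | 35.8% | 12.9% | 1.7% |
| 50% | 60.3% | 36.3% | 13.2% |
| 25% | 77.8% | 60.5% | 36.6% |
| 10% | 90.5% | 81.8% | 67.0% |
| 0% | 100% | 100% | 100% |

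Example: *n* = 40, *c* = 25% gives (1 − 0.05 × 0.25)^40 = 0.9875^40 = 0.605. With *n* = 40 and *c* = 25%, an assumed *p* of 1% gives 90.5% and *p* of 10% gives 36.3%. The chance of a clean record depends heavily on *c*, and without solicitation *c* is unknown.

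**The case against.** The strongest reply is that harm would not go unseen. Pain, PRTEE/DASH and the functional score are taken at all six contacts, pain and medication daily to week 8, and grip strength at enrollment, 8 weeks and 6 months. The medical record and case report forms are named as data sources, and the injections are routine care whose complications may well be charted. Study Oversight also offers data for monitoring or audit on request and says the investigators will address concerns. All of this stands. A reader might infer that the trial cannot detect harm, and the protocol does not support that: worsening pain, function or grip would be recorded. What these sources do not do is ask about events. Pain and function scores do not identify a skin reaction or attribute a cause, and no safety field is specified for the record or the forms.

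Three further inferences go too far:
- That a planned comparison of tolerability has been lost. No objective, hypothesis or outcome concerns safety.
- That the protocol is at fault for listing no events for the stem-cell component. The injections are chosen independently of the study, and the list of PRP reactions is not worded as complete.
- That a zero-event confidence limit measures the defect. With 40 solicited subjects the one-sided 95% limit is 1 − 0.05^(1/40) = 7.2%, but this assumes 1:1 allocation and describes the trial after the fix.

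It is also fair that a low-risk external sleeve calls for light oversight. That argues for proportion, not for none. Nor can the matter be left to an SAP, which cannot analyse what was not collected.

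**Conclusion.** The concern holds as a gap in systematic collection together with an internal inconsistency. No contact or log in Table 1 is scheduled to solicit adverse events, the AE/SAE subsection has a path only for confidentiality breaches, and oversight is set aside because no reason to stop is foreseen. Followed as written, an absence of recorded events would not be evidence of safety and could not bear out the premise that opens Section 7. The commitments to report unanticipated problems and to follow Good Clinical Practice are left without a scheduled means of discovery.

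The size is best stated as 0 of 8 schedule rows across six contacts and the daily logs. The illustrative probabilities rest on an assumed event rate, capture share and allocation. The finding is limited to the text at hand: case report forms and consent pages are not shown and may carry reporting instructions. It does not touch the validity of the primary PRTEE comparison, and is a change that should be made rather than one on which the trial depends.

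**What to change.** - Add an adverse-event row to Table 1, with one scripted question recording onset, severity and relatedness at the existing contacts at 2, 4 and 8 weeks and 3 and 6 months.
- Tabulate events by sleeve group within injection choice, so that events around the injections are not mixed with those of subjects who declined them.
- In Study Oversight, delete the clause that declares oversight not applicable, and state which role reviews the events and reports to the IRB. No monitoring board or stopping rule is asked for.
- Reconcile the three safety passages of Section 7 (the opening text, Monitoring/Reporting of AE/SAE and Study Oversight) with the Compliance Statement and the Good Clinical Practice commitment.

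The cost is one question at five contacts that already take place, one table in the report and a short amendment. The downside is slightly longer calls and visits and some paperwork.

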# **Data Management**

All study related data will be stored in a limited access folder that is on the PI's network. Some analysis of de-identified data may be conducted by Sponsor consultants, all of whom completed requisite human subjects and data protection training. All analysis will be conducted using Microsoft Excel or SPSS version 25.

### IRB Review/Ethics/Informed Consent

All potential participants will be provided a research subject consent form and time with their doctor to go over this form. Only subjects who are willing and able to sign the consent form will participate in the study. Subjects may choose to opt out of the study at any time and will be informed of this. Data collected for this study will be obtained from the patient electronic medical record (EMR), questionnaires completed by the subject, and in case report forms completed by the PI or study staff. This study is being conducted in accordance with the ethical principles that have their origin in the Declaration of Helsinki and that are consistent with Good Clinical Practice and applicable regulatory requirements. The study is being conducted in accordance with applicable regulations, applicable laws and the IRB requirements. The investigators will submit any change to the protocol to the IRB for review and approval before implementation.

